7. DOCUMENTATION AND DATA MANAGEMENT

Data collection in the case report form (CRF)

All study data will be recorded in the case report forms identified by the subject number. Only the principal investigator, co-investigators, or designated study personnel may make entries in the case report forms.

The Investigator has to identify all data that were directly recorded into the CRF and to be considered to be source data.

The CRFs will be checked for completeness and plausibility by the PI. The Investigator will resolve any queries.

Investigator Site File (ISF)

The ISF includes all documents that are required for the clinical study. During monitoring, the ISF will be checked regularly for completeness and actuality. After the clinical trial is finished or stopped, the ISF has to be stored 15 years in the study center.

Data Management

Data extraction from CRFs into a single, electronic database is performed by examiners. Discrepancies are to be clarified and corrected by authorized persons by means of documented data queries between Statistician and Investigator(s).

After the study is finished and before data are analyzed, a blind data review meeting will be held between the investigator and the statistician. When the database has been declared to be complete and accurate, it will be locked. Any changes to the database after this procedure can only be made by joint written agreement among the clinical trial leader, the trial statistician, and the co-investigators.

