1. STUDY DESIGN

The study design was chosen according to the current standards required by ISO, GCP and according to national requirements.

- a. A Parallel-Arm, Statistician is blinded, RCT will be established;
- b. The RCT will be run as mono-center;
- c. A total of 40 subjects will be recruited to participate in the study. It is expected that all of 34 subjects will complete the study in total;
- d. Admission into the study will be via rolling admission (estimated recruitment time: 12 months);
- e. Each subject must have posterior monoedentulia (mandibular or maxillary) intercalated;
- f. Each subject will follow the following treatment protocol:
 1. Visit 1: (Screening)
 - a. Screening and entry into study.
 - b. Verification of the eligibility of each subject by performing intraoral radiography.
 - c. Explanation of the research protocol.
 - d. Consent secured.
 - e. Delivery of the medical request for CBCT (cone beam computed tomography) and for the antibiotic (Amoxicillin 1000mg 2cp/die every 12 hours for 6 days or Azithromycin 500mg 1cp/die every 24 hours for 6 days).
 2. When CBCT is ready the patient have to give it to the Principal Investigator to confirm the eligibility of each subject and to plan the surgery. Professional dental hygiene session is performed before surgery.
 3. Visit 2: (Treatment)
 - a. Assessment of antibiotic prophylaxis, locoregional anesthesia and opening of a thickness flap limited to the intervention area.
 - b. According to the list of randomization the patient will be allocated into one of the two arm of surgical treatment. Group A (control group): placement of the endosseous crestal implant through dedicated drills with 35N insertion torque and healing abutment. Group B (test group): placement of the endosseous subcrestal implant (2 mm under crestal bone) through dedicated drills with 35N insertion

torque and GFA (Gingival Former Abutment). Both group receive the same implant: TZero® (L= 9 mm, Ø 3,6 mm or L= 7,5 mm, Ø 4,3 mm) (Advan S.r.l. [name])

- c. Suture.
- d. Execution of intra-oral and post-operative X-Rays.

After 7 days of the surgery suture removal.

- 4. Visit 3: (after 3 months from visit 2) (Treatment)
 - a. Periodontal charting around the healing abutment or GFA (PD, BOP, PI) with calibrated periodontal probe.
 - b. Impression taking for prosthetic finalization.
- 5. Visit 4: (after a week from Visit 3: Baseline – T0): (Treatment)

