 - a. Prosthetic finalization and loading.
 - b. Periodontal charting around the new prosthetic crown (PD, BOP, PI, REC).
 - c. Take a standardized x- Ray (Bite Block).
- 6. Visit 5 (6 months from baseline – T1): (Follow-up)
 - a. Control.
 - b. Periodontal charting around the prosthetic crown (PD, BOP, PI, REC).
 - c. Take a standardized x- Ray (Bite Block).
 - d. Professional dental hygiene session.
- 7. Visit 6 (12 months from baseline – T2):
 - a. Control.
 - b. Periodontal charting around the prosthetic crown (PD, BOP, PI ,REC).
 - c. Take a standardized x- Ray (Bite Block).
 - d. Professional dental hygiene session.
- g. All treatments are made by the same clinician;
- h. Data collection:
 - Standardized X- Ray: control periapical radiographs is performed using a long-cone paralleling technique and an individual X-ray holder (bite block) to ensure reproducibility. Built thanks to impression material.
 - A calibrated periodontal probe (Click-Probe™ Kerr Dental) is used on six sites per tooth (mesio-buccal, buccal, disto-buccal, mesio-lingual, lingual and disto-lingual) with a standard probing force by the same clinician. Measurements are rounded to the nearest millimeter;

- j. Clinical and radiographical assessment data will be recorded via hard copy CRFs. CRFs will be submitted to a data entry staff member for entry into the statistical database. At the conclusion of the study, such statistical database will be submitted to the statistician for the preparation of the statistical analysis and the final study report.
- k. Prosthetic finalization is given to the dental laboratory.

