2. TREATMENTS

Implant kit, implants and every component will be delivered to the study center prior study start by Advan S.r.l. [name]:

- Surgical Kit PRO: GKC13
- Set countersink GFA: GKM10
- Kit stop drills: GST11
- Implant: TZero - T3609 (D3,6 L9,0) - T4307 (D4,3 L7,5)
- GFA: 04GFX03 (D4,0 H3,5) - 04GFX04 (D4,0 H4,5) - 04GFX05 (D4,0 H5,5)
- component GFA: 01GFT01 (healing stopper H1) - 01GFT03 (healing stopper H3) -01GFT05 (healing stopper H5) - 01TGF10 (transfer pick-up) - 01AGF10 (analogo GFA) -01CGF40 (moncone calcinabile con base in cobalto-cromo)
- for control group: 05OMG12 (healing abutment H2) - 05OMG13 (healing abutment H3) - 05OMG14 (healing abutment H4) - 01OTR10 (transfer pick-up) - 41CCN40 (moncone calcinabile con base in cobalto-cromo)

Radiographically Analysis

Specification of software analysis

Peri-apical x-ray examinations will be performed using phosphor image plates (FONA™ Dental Image Plates) and then acquired through a digital scanner device (FONA ScaNeo™).

All radiographical images will be later analyzed by the same external examiner, which will measure marginal bone level parameter (MBL) around placed endosseous implants using an image analysis software (ImageJ™).

In particular bone levels will be determined, both mesially and distally the dental implant, using the “Measure” function of the software, which records the distance between the most apical bone point and the most coronal bone point in 0.3 mm range from the implant.

Measurements will be all recorded to allow the observation of bone level changes over time.

Concomitant Therapy

A necessary concomitant medication or therapy is permitted as long as it is not excluded in the exclusion criteria. Every medication has to be reported in the CRF (Appendix 1) and in the Concomitant Medication form (Appendix 2). All changes during the study are to be reported in the CRF. Usage of prohibited therapy will lead to the exclusion of the subject.

Blinding and Randomization

Blinding:

The statistician and the patient will be blinded to the group identification. The operator will know the treatment allocation. Knowledge of the randomization list will be limited to the persons responsible for creation of the randomization list, provider of randomization numbers to study site, and delivery of the test/control treatment until the last subject (i.e. final examination of the last subject), quality control and verification of the CRFs is completed.

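### The pre-analysis data review is called blind but includes an investigator whom the plan never blinds, and the restriction on the randomization list is not tied to that review or to the database lock

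*Combined protocol and SAP*

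**What the plan says.** Section 7 (Data Management) sets the timing of the review, "After the study is finished and before data are analyzed", and its parties: "a blind data review meeting will be held between the investigator and the statistician". The database is locked once it is declared complete and accurate. Changes after lock remain possible if the trial leader, the statistician and the co-investigators agree in writing. The same section has the investigator resolve CRF queries.

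Section 2 (Blinding and Randomization) says who is blinded: "The statistician and the patient will be blinded to the group identification". It adds: "The operator will know the treatment allocation". Knowledge of the randomization list is confined to a few named functions until the last subject's final examination has taken place and "quality control and verification of the CRFs is completed".

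The synopsis names only the statistician as blinded. So does section 1: "A Parallel-Arm, Statistician is blinded, RCT will be established". Section 1 also says that the trial has a single centre and that "All treatments are made by the same clinician".

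The Study Population section allows randomized subjects with a major protocol deviation to be excluded from the analysis and replaced. It does not define such a deviation, and does not say who decides or when. Section 4 defines a safety analysis set but no efficacy set.

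**The concern.** A blind data review protects the analysis only if those who settle exclusions and doubtful values do not know the arm. Here one of the two parties has no stated blind and probably knows the allocation. The other party, the statistician, is blinded, but the rule that guards the list ends at a milestone other than the database lock.

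By the time of the review, the follow-up data are in. If an exclusion is argued by someone who knows both arm and outcome, it can favour one arm without any visible breach of the protocol. With 34 patients planned for analysis, a few such decisions can matter. The plan leaves room for them, because the grounds for exclusion are undefined and no efficacy set is fixed in advance.

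**Working it through.** **Who is blinded**

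| Role | Status in the plan | Source |
|---|---|---|
| Statistician | Blinded | Synopsis; sections 1 and 2 |
| Patient | Blinded | Section 2 |
| Operator | Knows allocation | Section 2 |
| Any investigator | No blind stated | No section |

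The review joins the first and the last of these. That the investigator knows the arm is an inference. It rests on one centre, one treating clinician, and arms that differ visibly (crestal implant with healing abutment against an implant 2 mm subcrestal with GFA).

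**When the list restriction ends**

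- Section 2: after the last examination and after CRF quality control and verification.
- Section 7: review after the study ends and before analysis; lock when the database is declared complete and accurate.

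A database can hardly be declared complete and accurate before its CRFs are verified, so the restriction can end at or before the lock. The order of verification and review is not stated, so the restriction may end before or after the review.

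**The plan's own figures**

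Inputs from section 4: SD 0.5 mm, difference 0.5 mm, 5% significance, power at least 80%, independent-sample t-test, balanced groups. I assume a two-sided test.

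- Normal approximation: 2 × (1.96 + 0.84)² × 0.5²/0.5² = 15.7, so 16 per arm.
- t-test: 16.7, so 17 per arm, 34 in total, power 80.7%.
- Drop-out: 34/0.85 = 40.

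The sample size reproduces, and the point does not change it.

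**Illustration 1: changed values**

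Assumptions (mine): k = 1 to 3 patients of 17 in one arm have a value changed by 1 mm, all in one direction.

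- Shift in arm mean = k × 1/17 = 0.059, 0.118, 0.176 mm.
- Relative to 0.5 mm: 12%, 24%, 35%.
- Standard error of the difference = 0.5 × √(2/17) = 0.171 mm, so 0.34, 0.69, 1.03 standard errors.

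If patients whose values lie 1 mm from the full-arm mean are dropped instead, the shift is k/(17 − k) = 0.06, 0.13, 0.21 mm.

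**Illustration 2: worst-case exclusions**

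Assumptions: no true difference, normal data, SD 0.5 mm, 20 per arm, 100,000 simulated trials. Someone who knows arm and outcome removes the k patients least favourable to the test device, alternating arms.

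| k removed | Two-sided type I error |
|---|---|
| 0 | 5.0% |
| 1 | 6.9% |
| 2 | 11.6% |
| 3 | 17.6% |
| 4 | 25.9% |
| 6 (= 40 − 34) | 44.4% |

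With exclusions unrelated to outcome, leaving 17 per arm, the rate is 4.9%, which is nominal apart from simulation error.

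**The case against.** The best defence has four parts.

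1. *The review may fall inside the restricted period.* Statistician–investigator queries and the review can be read as part of CRF quality control, which would keep the list closed throughout. This stands. A reader might infer that the list is opened before the review, but the documents do not order the two steps. They support only that it can be.

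2. *Custody of the list is not the statistician's blind.* The statistician's blinding is stated separately and without an end date. This also stands. A reader might infer that the list passes to the statistician before lock, but nothing says so. What is missing is a rule that keeps the list restricted until lock.

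3. *Operator and investigator are different words.* The documents also mention co-investigators and a dental examiner, and do not say that the operator attends the review. It is therefore a strong inference, not stated text, that the investigator there knows the arm. The gap remains, because no investigator is blinded under any title.

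4. *There are safeguards, and the meeting has no stated agenda.* An external examiner measures MBL, and corrections go through documented queries, so a silent change at the meeting is not what the plan describes. That makes altered values less likely. It does not cover exclusions, for which the plan gives neither criteria nor a decision-maker.

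A reader might also take the review for the last point at which data can change. Section 7 rules that out by allowing agreed changes after lock.

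**Conclusion.** The point holds in a limited form. As written, the review is assured to be blind only on the statistician's side, and the restriction on the list can lapse before the review or the lock. Decisions on exclusions and queries can therefore be made by, or with, someone who knows the arm. This follows from the investigator's missing blind together with the strong inference that this person knows allocation. It does not depend on early release of the list.

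The documents do not give the size of any bias. The range of 0.06 to 0.18 mm depends on an assumed 1 to 3 patients and an assumed 1 mm each, which is two of the plan's own standard deviations. The simulated error rates are a worst case and not a forecast. Both show only that a handful of decisions can matter at this sample size. The change should be made because it is cheap and gives the plan the blind review it already intends.

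**What to change.** 1. **Section 2, Blinding and Randomization.** Keep the randomization list restricted until the database lock described in section 7 has been documented.
2. **Section 7, Data Management.** Have the blinded statistician make the exclusion and classification decisions from an arm-masked listing, with coded subject numbers and neither arm nor component codes. Component codes must go because section 2 lists different ones for each arm. Judge each case against major-deviation criteria fixed beforehand. The investigator supplies factual answers through the documented queries. Sign the decisions before lock and before list release. MBL plausibility checks can stay in the review if they are arm-masked.
3. **Section 7, changes after lock.** Log each change with its reason and whether those agreeing to it knew the arm.

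The cost is a few sentences, a set of deviation criteria written in advance, the work of masking the listing, and a list release that waits for lock. Sample size and treatment are unaffected.

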8. ADVERSE EXPERIENCES/EVENTS

Subjects will be informed of any possible adverse reactions which they could experience and will be instructed to immediately report any event to the investigator. The investigators will record any and all adverse reactions and report this documentation to the Principal Investigator. In the event of an adverse experience, emergency or other problems or questions regarding participation in this study, the subject can contact the following investigators:

[name] (Principal Investigator) – [contact].

Adverse Events (AEs) and Serious Adverse Events (SAEs) are defined by the ICH Guideline Medical Device Directive 93/43/EEC and Guidelines on Medical Devices MEDDEVG 2.7/3rev. 3, May 2015 Clinical Investigations: Serious Adverse Event Reporting under Directives 90/385/EEC and 93/42/EEC for Good Clinical Practice (ICH GCP) as follows:

An adverse event (AE) is any untoward medical occurrence, unintended disease or injury or any untoward clinical signs (including an abnormal laboratory finding) in subjects, users or other persons whether or not related to the investigational medical device.

With respect to intensity, adverse events are classified as follows:

- Mild Some awareness of symptoms, but easily tolerated;
- Moderate Symptoms causing enough discomfort to interfere with usual activity;
- Severe Incapacitating event causing inability to work or to perform usual activity.

Adverse events are classified as either non-serious or serious.

Serious Adverse Event (SAE) is an adverse event that:

- a) led to a death;
- b) led to a serious deterioration in health of the subject, that either resulted in:
 - a life-threatening illness or injury, or
 - a permanent impairment of a body structure or a body function, or
 - in-patient hospitalization or prolongation of existing hospitalization, or
 - in medical or surgical intervention to prevent life threatening illness or
 - injury or permanent impairment to a body structure or a body function.
- c) led to fetal distress, fetal death or a congenital abnormality or birth defect.

Device deficiency: inadequacy of an investigational medical device related to its identity, quality, durability, reliability, safety or performance. This may include malfunctions, use error, or inadequacy in the information supplied by the manufacturer.

AEs include any clinically significant deterioration of a subject's medical status, after being enrolled and signing an informed consent form. The AE may involve any organs or systems and can be represented by the new onset or the deterioration of a disease, a syndrome, a symptom, a physical sign, as well as by findings and results of instrumental examinations and laboratory tests. Any medically relevant and untoward change from baseline, including frequency or pattern changes for a fluctuating condition (e.g., migraine), occurring after the administration of investigated treatments is an adverse event. All such occurrences must be recorded and reported accordingly, whether they appear causally related to the study medication, or not.

Serious Adverse Device Effect (SADE) is an adverse device effect that has resulted in any of the consequences characteristic of a serious adverse event.

Unanticipated Serious Adverse Device Effect (USADE) is a serious adverse device effect which by its nature, incidence, severity or outcome has not been identified in the current version of the risk analysis report or investigator's brochure (IB).

NOTE: Anticipated SADE (ASADE): an effect which by its nature, incidence, severity or outcome has been previously identified in the risk analysis report or IB.

The following events are considered reportable:

- any SAE;
- any Device Deficiency that might have led to a SAE if:
 - a) suitable action had not been taken or
 - b) intervention had not been made or
 - c) if circumstances had been less fortunate;
- new findings/updates in relation to already reported events.

Reportable events have to be reported by clinical investigators.

Assessment of Causality

The following criteria are to be used for the assessment of the causal relationship to the test/control treatment. For classification, all criteria of one of the following categories must be met:

related, if

- a timely correlation exists and
- dechallenge and/or rechallenge and
- a biological plausibility exists and
- other factors are clearly excluded
- a medical report or clinical proof exists;

possibly related, if

- a timely correlation exists and
- dechallenge and/or rechallenge and
- a biological plausibility exists and
- a medical report or clinical proof does not exist;

unrelated, if

- a timely correlation does not exist or is uncertain and
- dechallenge and/or rechallenge does not exist and
- a biological plausibility exists and
- a medical report or a clinical proof does not exist;

unknown, if

- not enough information exists for evaluation

- no further contact with reporter possible.

Sound medical/clinical judgment will be applied when assessing the causality and seriousness of the adverse events.

Adverse Event Reporting

The study center will provide the study participants with emergency telephone numbers for study related support and feedback. The emergency telephone number is operated by either an investigator of the study or by a qualified person designated by the principal investigator. The schedule of reachability of the emergency telephone number will be defined prior to start of the study.

Serious Adverse Events

The Investigator shall immediately after awareness (and in any event, not later than within 24 hours after awareness) inform the PI. The Investigator will send the SAE report to the following email address: [contact]. Appendix 3 has to be used for SAE reporting. Form has to be completed electronically and in English.

Adverse Events

Adverse events will be assessed by the investigator or designee within 24 hours for severity, relationship to the study product, possible etiologies, and whether the event meets the criteria as a serious adverse event and therefore requires immediate notification to the PI. For data collection purposes, the outcome of all adverse events recorded on the Adverse Reaction section of the CRF will be designated as of the completion of the final evaluation or examination. However, the investigator is responsible for following all adverse events until resolution or until no longer of clinical concern, and providing these data to the PI. At the end of the study, the investigator will report all adverse events (serious and non-serious) to the PI on CRFs. Forms have to be completed electronically and in English.

Pregnancy

No pregnant women (according to medical history) will intentionally be enrolled in this study. In the event a woman enrolled in this clinical research study becomes pregnant during the course of the study, participation in this study will be terminated upon the clinical staff's notification of the event.

The subject's medical records used in this study will be updated to reflect the pregnancy and there will be follow- up contact until the end of the pregnancy to record the outcome in the clinical file.

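### Minor: read literally, the adverse-event causality list leaves some timely, plausible events in no category, so the planned count of AEs at least possibly related can be too low

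*Combined protocol and SAP*

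**What the plan says.** Protocol section 8, Assessment of Causality, defines four categories and sets one rule for using them: "For classification, all criteria of one of the following categories must be met".

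- **Related** needs a timely correlation, "dechallenge and/or rechallenge and" biological plausibility; it also needs that "other factors are clearly excluded" and that a medical report or clinical proof is available.
- **Possibly related** needs the same first three items, and that "a medical report or clinical proof does not exist".
- **Unrelated** begins with "a timely correlation does not exist or is uncertain and" then requires that there is no dechallenge or rechallenge, that "a biological plausibility exists and" that there is no report or proof.
- **Unknown** needs too little information for an evaluation and "no further contact with reporter possible".

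The list closes with: "Sound medical/clinical judgment will be applied when assessing the causality and seriousness of the adverse events".

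The categories feed section 4, Evaluation of Safety. It plans, for each treatment group, the total number of AEs, the number judged at least possibly related to treatment, and the number of patients with at least one AE.

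**The concern.** A classification that demands every criterion of a category works only if each event can satisfy some category in full. This list does not ensure that. Its two positive categories share a dechallenge/rechallenge requirement with no exception for events where it was not done or does not apply. The proof criterion then works against itself: if an event is 'possibly related' and other causes are not clearly excluded, adding medical proof removes it from that category without making it 'related'.

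At stake is the per-group number of related AEs, which is one of the few safety summaries the plan prespecifies. An event with no category cannot be counted as at least possibly related. The same holds if an assessor puts it under 'unknown' for want of anything better.

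**Working it through.** The plan gives no figure to reproduce here; the check is one of logic.

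**Inputs (section 8, Assessment of Causality).** Five yes/no criteria: T, timely correlation (no = absent or uncertain); D, dechallenge and/or rechallenge; B, biological plausibility; O, other factors clearly excluded; M, medical report or clinical proof. Information is taken as sufficient, so 'unknown' does not apply. The D line has no verb in the two positive categories; I read it as 'exists', because the 'unrelated' list says that it does not exist.

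**Rules as written.**
- Related = T and D and B and O and M
- Possibly related = T and D and B and not M
- Unrelated = not T and not D and B and not M

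**Timely and plausible events (T = yes, B = yes): 2 × 2 × 2 = 8 profiles.** The last column applies the rewording given under the fix.

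| D | O | M | As written | After the fix |
|---|---|---|---|---|
| yes | yes | yes | related | related |
| yes | yes | no | possibly related | possibly related |
| yes | no | no | possibly related | possibly related |
| yes | no | yes | none (b) | possibly related |
| no | yes | yes | none (a) | possibly related, or related if D is not applicable |
| no | yes | no | none (a) | possibly related |
| no | no | yes | none (a) | possibly related |
| no | no | no | none (a) | possibly related |

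As written, 3 of 8 are classified and 5 are not: 4 of type (a) and 1 of type (b). The four type (a) rows fail both positive categories on D and fail 'unrelated' on T. The type (b) row fails 'related' on O, 'possibly related' on M and 'unrelated' on T.

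**Full grid, 2^5 = 32 profiles.** As written: 1 related, 2 possibly related, 2 unrelated, and 32 − 5 = 27 in no category. Of the 27, 5 are the rows above; the other 22 lack timing or plausibility.

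**After the fix.** All 8 timely and plausible profiles are classified: 1 related and 7 possibly related, or 2 and 6 if 'no dechallenge' means not applicable. 'Unrelated' becomes not T and not D and not M, which is 2 (B) × 2 (O) = 4 profiles instead of 2. None of the 5 profiles classified now changes category. The remaining 32 − 8 − 4 = 20 all lack timing or plausibility and stay unclassified; this is why the fix asks for their number to be reported.

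**The plausibility line in 'unrelated'.** As written, an event with no timing, no dechallenge, no proof and no plausibility cannot be called unrelated. This looks like a dropped 'not'. It does not change the related count.

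**The case against.** The best defence is that nobody would apply the list so mechanically. Section 8 calls for clinical judgment on causality. It also has each AE assessed within 24 hours for its relationship to the product and its possible causes, so every event is meant to receive a rating. Section 7 adds a check of the CRFs by the principal investigator and a blind data review before analysis. The bullets themselves are incomplete, which argues against reading them as strict logic. This stands in part: loss of events is a risk of the wording, not a certainty. It does not close the gap, because none of these provisions names a category for an event that meets none in full, and none sets aside the all-criteria rule.

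A reader might go further than the documents allow in three ways.

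- **That 27 of 32 measures the size of the problem.** It does not. Profiles are not equally likely, 22 of the 27 lack timing or plausibility, and the documents give no AE rate. The number of events affected could be zero.
- **That type (a) must be the usual case, because a placed implant is not readily withdrawn.** The protocol does not define dechallenge, and section 4 foresees AEs that lead to discontinuation or withdrawal of treatment. How often dechallenge would be lacking cannot be read from the documents.
- **That the comparison between arms is biased.** The same list applies to both groups. The operator knows the allocation (section 2, Blinding), but nothing shows that uncategorised events would fall more in one arm.

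**Conclusion.** The point holds as a minor one: the stated rule is wrong as written and cheap to correct. Under literal use, 5 of the 8 timely and plausible profiles have no category and drop out of the section 4 count of AEs at least possibly related, so that count can be too low.

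The effect is confined to that single descriptive count. Total AEs, patients with any AE and the organ-system tables do not use the causality rating. SAEs are reportable whatever their cause (sections 2 and 8). The primary MBL analysis is not involved.

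The conclusion rests on three assumptions: the all-criteria rule is applied as stated, the verbless dechallenge line means that dechallenge or rechallenge exists, and information on the event is sufficient. Confidence in the logical gap is high; its practical frequency is unknown.

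**What to change.** Reconcile the list in section 8 with the count in section 4:

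1. **Related:** keep the present criteria, with dechallenge/rechallenge required only where applicable.
2. **Possibly related:** timely correlation and biological plausibility exist, but not all criteria for 'related' are met.
3. **Unrelated:** remove the line that requires biological plausibility.
4. **Reporting:** beside the related count, give per group the number of AEs rated 'unknown' or left unclassified.

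A catch-all that sends almost every unclassified event to 'possibly related' is tempting but over-corrects. If 'unrelated' took only events with no dechallenge, no proof, and timing or plausibility missing (3 × 2 = 6 profiles), the other 26 of 32 would be at least possibly related, against 3 now. That includes 6 with neither timing nor plausibility. The narrower wording gives 8, exactly the timely and plausible ones.

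Cost: a short protocol amendment under section 9, with no extra visit or measurement. The CRF and SAE forms are not in the documents, so any change to them cannot be judged. The related count may be somewhat higher, because a timely, plausible event with another likely cause will count as possibly related.
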